8.2 Participant demographics/other baseline characteristics

Country-specific regulations should be considered for the collection of demographic and baseline characteristics in alignment with CRF.

Participant demographics: age (in years), sex, race/predominant ethnicity (if permitted) and relevant medical history/current medical conditions (until date of signature of informed consent) will be recorded in the eCRF. Participant race/ethnicity data are collected and analyzed to identify any differences in the safety and/or efficacy profile of the treatment due to these characteristics. In addition, these data are necessary to assess the diversity of the study population as required by health authorities.

All prescription medications, over-the-counter drugs and significant non-drug therapies prior to the start of the study must be documented up to 6 months before the study. See also the protocol [Section 6.8.1](#) Concomitant Therapy for further details on what information must be recorded on the appropriate page of the eCRF.

To determine the eligibility for inclusion in the study, serum creatinine, eGFR and surgery information will be collected and recorded in the eCRF.

8.2.1

CCI

CCI

8.3 Efficacy assessments

Planned time points for all efficacy assessments are provided in [Section 1.3](#) Schedule of Activities.

Pharmacodynamic (PD) samples will be collected at the time points defined in [Section 1.3](#) Schedule of Activities. Follow instructions outlined in the Laboratory manual regarding sample collection, numbering, processing, and shipment.

Pharmacodynamic samples will be obtained and evaluated in all participants at all dose levels, including the placebo group.

8.3.1 Serum Creatinine

Serum creatinine is a standard marker to assess renal function and diagnose AKI. Serum creatinine samples will be collected from participants at all visits from baseline to Day 90/EOS.

8.3.2 AKI incidence and severity

AKI incidence over the first week after surgery will be measured using the modified AKIN classification system, based on changes in serum creatinine compared to pre-operative value. Severity of AKI will be assessed using three stages, with stage 1 being the less severe and stage 3 the more severe (see [Table 8-1](#)).

CCI

CCI

Table 8-1 The modified AKIN classification system of acute kidney injury

Stage	Serum Creatinine/RRT
1	Serum creatinine (SCr) ≥ 1.5 - < 2.0 x baseline within 7 days post-surgery Or \uparrow SCr by ≥ 26.5 $\mu\text{mol/L}$ (≥ 0.3 mg/dL) within 2 days post-surgery
2	SCr ≥ 2.0 - < 3.0 x baseline within 7 days post-surgery
3	SCr ≥ 3.0 x baseline within 7 days post-surgery Or \uparrow SCr to ≥ 353.6 $\mu\text{mol/L}$ (4.0 mg/dL) AND by ≥ 44.2 $\mu\text{mol/L}$ (0.5 mg/dL) within 7 days post-surgery Or ^a Initiation of RRT within 7 days post-surgery

\uparrow Increase from baseline

^aStage 3 includes patients requiring RRT independent of the AKI stage they are in at the moment of RRT initiation.

Adapted from ([Barry, James 2015](#))

Table 8-2 The kidney disease improving global outcomes (KDIGO) classification

Stage	Serum Creatinine/RRT
1	SCr 1.5-1.9 x baseline within 7 days post-surgery Or \uparrow SCr by ≥ 0.3 mg/dL (≥ 26.5 $\mu\text{mol/L}$) within 2 days post-surgery
2	SCr 2.0-2.9 x baseline within 7 days post-surgery
3	SCr ≥ 3.0 x baseline within 7 days post-surgery Or \uparrow SCr to ≥ 4.0 mg/dL (≥ 353.6 $\mu\text{mol/L}$) AND by ≥ 0.5 mg/dL within 7 days post-surgery Or Initiation of RRT

\uparrow Increase from baseline

Table 8-3 The RIFLE (Risk, Injury, Failure, Loss of kidney function, and End-stage kidney disease) classification

Class	Serum Creatinine/GFR
Risk	SCr 1.5 x baseline or ↓ eGFR >25%
Injury	SCr 2 x baseline or ↓ eGFR >50%
Failure	SCr 3 x baseline or ↓ eGFR >75% Or ↑ SCr to ≥353.6 μmol/L (≥4 mg/dL) AND by >44.2 μmol/L(>0.5 mg/dL)
Loss of kidney function	Complete loss of kidney function >4 weeks
End-stage kidney disease	Complete loss of kidney function >3 months

SCr = serum creatinine, eGFR = estimated glomerular filtration rate

↑ Increase from baseline, ↓ decrease from baseline

8.3.3 Major Adverse Kidney Event (MAKE)

The proportion of participants having major adverse kidney event at Day 30 (MAKE30) and 90 (MAKE90) will be assessed using the following components: 1) death, 2) initiation of renal replacement therapy, 3) ≥25% reduction in eGFR.

Information on death such as date of occurrence and cause will be captured in the eCRF.

In case a participant needs to receive renal replacement therapy, information will be collected in the eCRF, such as date, duration, method of dialysis and number of sessions.

eGFR will be calculated as described in [Section 8.3.4](#).

8.3.4 Estimated glomerular filtration rate (eGFR)

The eGFR 2021 CKD EPI creatinine equation that estimates kidney function without a race variable should be used for eGFR calculations during this study. A taskforce of members from the National Kidney Foundation NKF and American Society of Nephrology ASN assessed the accuracy of a new eGFR equation that incorporates creatinine but omits race, and concluded the new equation to be more accurate. Immediate implementation in all US labs was recommended in November 2021.

$$eGFR = 142 \times \min(SCr / \kappa, 1)^\alpha \times \max(SCr / \kappa, 1)^{-1.200} \times 0.9938^{Age} \times 1.012 \text{ [if female]}$$

where: SCr is serum creatinine in mg/dL, κ is 0.7 for females and 0.9 for males, α is -0.241 for females and -0.302 for males, min indicates the minimum of SCr / κ or 1, and max indicates the maximum of SCr / κ or 1.

The equation does not require weight because the results are reported normalized to 1.73 m² body surface area, which is an accepted average adult surface area.

8.3.5 Appropriateness of efficacy assessments

Serum creatinine is a standard marker used to assess renal function and diagnose AKI ([Ronco et al 2019](#)).

MAKE is a composite endpoint including death, need for RRT and worsening renal function (eGFR > 25% reduction from baseline). It can be assessed at defined intervals/timepoints and is increasingly being recognized as an important patient centered outcome from studies in patients who are critically unwell ([Billings, Shaw 2014](#)).

8.4 Safety assessments

Safety assessments are specified below with [Section 1.3](#) Schedule of Activities detailing when each assessment is to be performed.

For details on AE collection and reporting, refer to [Section 8.6](#).

As per [Section 4.5](#), during a public health emergency as declared by local or regional authorities i.e. pandemic, epidemic or natural disaster, that limits or prevents on-site study visits, regular phone or virtual calls can occur (every 4 weeks or more frequently if needed) for safety monitoring and discussion of the participant's health status until it is safe for the participant to visit the site again.

8.4.1 Physical examinations

A complete physical examination will include the examination of general appearance, skin, neck (including thyroid), eyes, ears, nose, throat, lungs, heart, abdomen, back, lymph nodes, extremities, vascular, and neurological. If indicated based on medical history and/or symptoms, rectal, external genitalia, breast, and pelvic exams will be performed.

Height in centimeters (cm) and body weight (to the nearest 0.1 kilogram (kg) in indoor clothing, but without shoes) will be measured.

Body mass index (BMI) will be calculated using the following formula:

- $BMI = \text{Body weight (kg)} / [\text{Height (m)}]^2$

The Screening Visit height measurement will be used for BMI calculations throughout the study.

Investigators should pay special attention to clinical signs related to previous serious illnesses.

Information for all physical examinations must be included in the source documentation at the study site. Clinically relevant findings that are present prior to signing informed consent must be recorded on the appropriate CRF that captures medical history. Significant findings made after signing informed consent which meet the definition of an Adverse Event must be recorded as an adverse event.

8.4.2 Vital signs

Vital signs will include the collection of body temperature (recorded in °C), blood pressure (BP) and pulse measurements.

Vital signs should be measured in sitting position whenever possible and measured in supine position if this is not possible especially early after surgery. After the participant has been sitting

for 3 minutes, with back supported and both feet placed on the floor, or just in supine position, systolic and diastolic BP will be measured using an automated validated device, with an appropriately sized cuff. In case the cuff sizes available are not large enough for the participant's arm circumference, a sphygmomanometer with an appropriately sized cuff may be used.

If vital signs are at screening (see Inclusion Criteria of the protocol for details), two additional readings can be obtained, so that up to three consecutive assessments are made, with the participant seated quietly for approximately five minutes preceding each repeat assessment. The last reading must be within the ranges provided in the eligibility criteria in order for the participant to qualify.

In case of repeated vital assessments, the eCRF should contain the qualifying results.

8.4.3 Electrocardiograms

The Fridericia QT correction formula (QTcF) must be used for clinical decisions, e.g., at the Screening visit to assess eligibility. The Investigator must calculate QTcF if it is not auto-calculated by the ECG machine.

ECGs will be locally collected and evaluated. Interpretation of the tracing must be made by a qualified physician and documented on the appropriate CRF. Each ECG tracing should be labeled with the study number, participant initials (where regulations permit), participant number, date, and kept in the source documents at the study site. Clinically significant abnormalities present at screening should be reported on the appropriate CRF. Clinically significant findings must be discussed with Novartis prior to enrolling the participant in the study. New or worsened clinically significant findings occurring after informed consent must be recorded as adverse events.

The original ECGs and a certified copy on non-heat sensitive paper, appropriately signed, must be archived at the study site.

Additional, unscheduled, safety ECGs may be repeated at the discretion of the Investigator at any time during the study as clinically indicated. For any ECGs with participant safety concerns, two additional ECGs must be performed to confirm the safety finding.

Clinically significant abnormalities must be recorded on the CRF as either medical history/current medical conditions or adverse events as appropriate.

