10. CCI [REDACTED]
11. Duration of cardiopulmonary bypass (CPB) <60 minutes.
12. Patient with active bleeding at the end of surgery as per assessment of the leading surgeon.
13. Use of other investigational drugs at the time of enrollment, or within 5 half-lives of enrollment, or until the expected PD effect has returned to baseline, whichever is longer; or longer if required by local regulations.
14. History of hypersensitivity to any of the study treatments or its excipients or to drugs of similar chemical classes.
16. Patients who are post-nephrectomy.
17. Any significant QT prolongation as per PI judgment and/or concomitant use of agents known to prolong the QT interval unless they can be discontinued or replaced by safe alternative for the duration of study (at the discretion of the investigator).
18. Taking medications prohibited by the protocol (see [Table 6-3](#) (Prohibited medications)).
19. History of malignancy of any organ system (other than localized basal cell carcinoma of the skin or *in-situ* cervical cancer), treated or untreated, within the past 5 years, regardless of whether there is evidence of local recurrence or metastases.
20. Donation or loss of >450 mL of blood or > 200 mL of plasma within four weeks prior to dosing, or longer if required by local regulation.
21. Have a history of any organ or cellular transplant which requires active immunosuppressive treatment which can interfere with kidney function (e.g., calcineurin inhibitors).
22. Have ongoing sepsis or history of sepsis within the past 8 weeks or untreated diagnosed infection prior to screening visit. Sepsis is defined as presence of a confirmed pathogen, along with fever or hypothermia, and hypoperfusion or hypotension.
23. Heart failure stage IV as defined by the New York Heart Association (NYHA) Functional Classification.

24. Left ventricular ejection fraction of $< 30\%$ as per most recent echocardiography available.
25. Recent (within the last three years) and/or recurrent history of autonomic dysfunction (e.g., recurrent episodes of fainting, palpitations, etc.).
26. Any surgical or medical condition which might significantly alter the absorption, distribution, metabolism, or excretion of drugs, or which may jeopardize the participant in case of participation in the study. The Investigator should make this determination in consideration of the participant's medical history and/or clinical or laboratory evidence of any of the following:

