## **2.7.4 Other safety data**

### **2.7.4.1 ECG and cardiac imaging data**

PR, QRS, QT, QTcF, RR intervals and Mean heart rate (HR) will be obtained from 12-lead ECGs for each participant during the study. CCI

Categorical analysis of QT and QTcF interval data based on the number of participants meeting or exceeding predefined limits in terms of absolute QT/QTcF intervals or changes from baseline will be presented. This categorical analysis will be based on post-baseline visits. In addition, a listing of these participants will be produced by treatment groups.

- QT, QTcF
  - Absolute value of > 450 and ≤ 480 ms
  - Absolute value of > 480 and ≤ 500 ms
  - Absolute value of > 500 ms
  - Increase from baseline by > 30 ms to ≤ 60 ms
  - Increase from baseline by > 60 ms
- PR
  - Increase from baseline by >25% and to a value > 200 ms
  - Absolute value of > 200 ms and ≤ 220ms
  - Absolute value of > 220 ms
- QRS
  - Increase from baseline by >25% and to a value > 110 ms
  - Absolute values of QRS > 110 ms and ≤ 120ms
  - Absolute values of QRS > 120

- HR
  - Increase from baseline by >25% and to a value > 100 bpm
  - Decrease from baseline by >25% and to a value < 50 bpm

All ECG data will be listed by treatment group, participant, and visit/time; abnormalities will be summarized and flagged based on the criteria above. All ECG data will be summarized by treatment group and visit/time. A box plot will also be created for ECG parameters over time by treatment groups. For each treatment group, individual participant spaghetti plots will also be created for ECG parameters.

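### The SAP's absolute ECG outlier rows carry no visible baseline condition, so participants already above a limit before surgery are mixed with newly occurring cases

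*Protocol*

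**What the plan says.** SAP 2.7.4.1 lists the criteria for the categorical ECG analysis.

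- **Absolute rows.** QT and QTcF share three bands: the first is "Absolute value of > 450 and ≤ 480 ms", followed by above 480 up to 500 ms and above 500 ms. PR has "Absolute value of > 200 ms and ≤ 220ms" and above 220 ms. QRS has above 110 up to 120 ms and above 120 ms.
- **Baseline-relative rows.** QT and QTcF have "Increase from baseline by > 30 ms to ≤ 60 ms" and a rise above 60 ms. PR has "Increase from baseline by >25% and to a value > 200 ms". QRS has the same 25% rule with a 110 ms limit. Heart rate has only baseline-relative criteria.
- **Timing.** "This categorical analysis will be based on post-baseline visits". The visible text does not say whether a participant is classified by the worst value or visit by visit.

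SAP 2.1.1 sets the safety baseline as the last non-missing assessment before surgery starts. In the Protocol's schedule of activities (Section 1.3) the only ECG before dosing is at screening (Day -30 to -1). ECGs follow at 8, 24, 48 and 72 hours and on Days 8, 30 and 90.

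At entry, Protocol 5.2 exclusion 17 removes "Any significant QT prolongation as per PI judgment", with no limit in milliseconds. No visible criterion addresses a long PR or a wide QRS.

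For adverse events, Protocol 8.4.3 says "New or worsened clinically significant findings occurring after informed consent must be recorded as adverse events".

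**The concern.** An absolute post-baseline category answers a clear safety question only if the reader can tell who entered it during the study. Participants here are at least 45 years old and about to have major cardiac surgery, so some can be expected to start with a PR above 200 ms, a QRS above 110 ms or a QTcF above 450 ms. In the visible text such a participant is counted after baseline in the same row, and in the same way, as someone who was normal at baseline and crossed the limit after dosing.

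A fixed pre-existing component inflates the count in every group and dilutes any difference. It also adds chance variation between groups, because about 120 participants are spread over placebo and two doses that are reported separately. ECG safety is part of a secondary endpoint in the first trial of this drug in patients, so a readable outlier table is worth having.

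**Working it through.** **1. No plan figure to reproduce.** Neither document states an expected rate of ECG abnormality, and the sample size sections are redacted. All rates below are assumptions.

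**2. Do the baseline-relative rows catch every new crossing?** They do not. Let b be the baseline value.

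- PR: a new value above 200 ms escapes the relative row if it is no more than 1.25b. That is possible for any b above 200/1.25 = 160 ms. Example: 185 to 225 ms is 40/185 = 21.6%. It crosses both PR limits and misses the row, which would need more than 1.25 × 185 = 231 ms.
- QRS: the same gap opens for b above 110/1.25 = 88 ms. Example: 100 to 122 ms is a 22% rise and crosses both QRS limits.
- QTcF: a new value above 450 ms with a rise of 30 ms or less is possible for b above 450 − 30 = 420 ms.

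Such crossings appear only in the absolute rows, alongside pre-existing cases.

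**3. How much of an absolute row could be pre-existing?** Let p0 be the share above the limit at baseline that stays above, and q the new-onset share among the rest. With N = 120 for illustration:

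expected count = N × [p0 + (1 − p0) × q]; pre-existing share = p0 / [p0 + (1 − p0) × q]

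| p0 | q | Counted | Pre-existing | New | Pre-existing share |
|---|---|---|---|---|---|
| 5% | 20% | 28.8 | 6.0 | 22.8 | 21% |
| 5% | 10% | 17.4 | 6.0 | 11.4 | 34% |
| 10% | 10% | 22.8 | 12.0 | 10.8 | 53% |
| 20% | 10% | 33.6 | 24.0 | 9.6 | 71% |
| 30% | 10% | 44.4 | 36.0 | 8.4 | 81% |
| 30% | 5% | 40.2 | 36.0 | 4.2 | 90% |

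**4. A second illustration, with repeated measurement.** Simulation of 400,000 participants, one baseline and seven post-dose ECGs, no drug or surgery effect. A participant counts if the worst post-dose value exceeds the limit.

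| Limit | Assumed mean; between-person SD; within-person SD (ms) | Counted | Of those, already above at baseline |
|---|---|---|---|
| QTcF > 450 | 425–440; 20–25; 10 | 29–57% | 41–62% |
| QRS > 110 | 100; 18; 4 | 40% | 72% |
| PR > 200 | 170; 28; 8 | 25% | 58% |

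This covers only the lowest limit for each interval. Even with no effect, some participants newly cross through measurement variation: for QRS 40% × (1 − 0.72) = 11% of all participants, and for PR 25% × (1 − 0.58) = 10.5%. Removing pre-existing cases therefore sharpens the rows but does not replace the comparison with placebo.

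**5. Chance imbalance.** If 20% are above a limit at baseline, and assuming 40 per group (the allocation ratios are redacted), the standard error of the between-group difference in that share is √(2 × 0.2 × 0.8 / 40) = 0.089, about 9 percentage points.

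**The case against.** The strongest reply is that the list already separates worsening from pre-existing abnormality through its change-from-baseline rows. ECG data are also summarised by visit and listed by participant, and the counts are descriptive, with a randomised placebo group. Protocol 9.4.1 prespecifies categories on absolute QT/QTc values or on changes from baseline, so the SAP has not departed from the Protocol. Exclusion 17 narrows the QT problem. Part of the ECG paragraph is redacted in both documents, so a further rule may exist there. Much of this stands and limits the point to the absolute rows. It does not remove the point, because step 2 shows new crossings that the relative rows miss.

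Four stronger readings are tempting and are not supported:

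- **Pre-existing abnormality is reported as an adverse event.** It is not. The rule in Protocol 8.4.3 governs adverse event recording, not this table, and SAP 2.7.1 requires onset from Day 1 or an increase in severity. The SAP never labels the absolute counts new or treatment-emergent.
- **The ECG outlier counts mostly measure baseline disease.** This ignores the relative rows. Even for the absolute rows the share depends on assumptions and can be well below half (21% in step 3, 41% in step 4).
- **Tabulating uncorrected QT hides a signal.** Protocol 8.4.3 says "The Fridericia QT correction formula (QTcF) must be used for clinical decisions", which concerns decisions, not tables. Take QTcF rising from 430 ms at 60 beats/min to 490 ms at 90 beats/min. Uncorrected QT goes from 430 to 490 × (60/90)^(1/3) = 428 ms, so the QT rows show nothing. The QTcF rows still do: the participant falls in the band above 480 up to 500 ms and in the row for a rise above 30 up to 60 ms.
- **QTcF counts must be restricted to narrow QRS.** Nothing in the documents requires this. It is a preference.

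**Conclusion.** The point holds for the absolute QT/QTcF, PR and QRS rows of SAP 2.7.4.1. They have no visible baseline condition and no shift table, so pre-existing and newly occurring cases cannot be told apart within a row. The relative rows reduce the loss without closing it. The size is not known from the documents: under the assumed rates in step 3, pre-existing cases make up 21% to 90% of a row. Randomisation balances these cases in expectation, so a difference between groups from this source would arise by chance. A reader might infer a systematic bias, but the documents do not support that. Placebo is pooled across both protocol periods and so is not fully concurrent with either dose, which is a reason to show baseline status but does not demonstrate bias. No visible decision rule depends on these rows. This is a cheap improvement to a safety table, subject to what the redacted text may contain.

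**What to change.** In SAP 2.7.4.1:

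1. Report each absolute category as newly occurring: the participant's last pre-surgery ECG was not in that or a higher category. Use participants below the cut-off at baseline as the denominator, and show those already above in a separate row. Equivalently, add a shift table from baseline category to worst post-baseline category, by treatment group.
2. State that the worst post-baseline value classifies the participant.
3. Keep the baseline-relative rows as they are.

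The ECGs are already collected, so the cost is SAP wording and programming. The downside is slightly smaller denominators in the newly-occurring rows and one extra table.

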8.4.4 Oxygen saturation

CCI

8.4.5 Clinical safety laboratory tests

Local laboratories will be used for analysis of all safety specimens collected (see [Table 8-4](#)).

As per [Section 4.5](#), during a public health emergency as declared by local or regional authorities' i.e., pandemic, epidemic or natural disaster, that limits or prevents on-site study visits, if participants cannot visit the site for protocol-specified safety lab assessments, an alternative lab (local) collection site may be used.

Clinically significant abnormalities must be recorded as either medical history/current medical conditions or adverse events as appropriate.

All abnormal lab results must be evaluated for criteria defining an adverse event and reported as such if the criteria are met. For those lab adverse events, repeated evaluations are mandatory until normalization of the result(s) or until the result is no longer considered to be clinically significant.

In the case where a laboratory range is not specified by the protocol, but a value is outside the reference range for the laboratory at screening and, a decision regarding whether the result is of clinical significance or not shall be made by the Investigator (in consultation with Novartis) and shall be based, in part, upon the nature and degree of the observed abnormality. The assessment may be repeated once prior to randomization.

In all cases, the Investigator must document in the source documents, the clinical considerations (i.e. result was/was not clinically significant and/or medically relevant) in allowing or disallowing the participant to continue in the study.

Fresh spot urine should be collected for urine assessments, e.g., urinalysis, CCI [REDACTED]. For patients with a urine catheter in place, the fresh urine should be obtained from the catheter sampling port. For patients without a catheter, a mid-stream (spot) urine should be collected for the sample (first morning void should be avoided).

Table 8-4 Local Laboratory evaluations

Test Category	Test Name
Full Hematology	Erythrocytes, Erythrocyte indices (MCH - Mean Corpuscular Hemoglobin, MCHC - Mean Corpuscular Hemoglobin Concentration, MCV - Mean Corpuscular Volume, Erythrocyte Morphology*), Hematocrit, Hemoglobin, Free Heme*, Platelets, Platelet indices (Platelet clumps count*, MPV - Mean Platelet Volume*), Leukocytes, Leukocyte Differential (Basophils, Eosinophils, Lymphocytes, Monocytes, Neutrophils, Band Neutrophils)
Limited Hematology	Leucocytes, Erythrocytes, Platelets, Hematocrit, Hemoglobin
Full Clinical Chemistry	Albumin, Alkaline phosphatase (ALP), Alanine Transaminase (ALT), Amylase (total), Aspartate Transaminase (AST), Bicarbonate (from venous blood), Total Bilirubin, Direct Bilirubin (conjugated), Indirect Bilirubin (unconjugated), Calcium, Chloride, Creatine Kinase (CK), Gamma-glutamyl-transferase (GGT), *Glutamate-dehydrogenase (GLDH), Glucose (fasting or non-fasting**), Lactate dehydrogenase (LDH), Lipase, Magnesium, Phosphate, Potassium, Sodium, Total Protein, Urea Nitrogen (BUN or Urea), Uric Acid, N-terminal pro b-type natriuretic peptide (NT-proBNP [#] , High-sensitivity C-reactive Protein (hs-CRP) [#] , high-sensitivity cardiac troponin [#] (preferentially I (hs-cTnI), but T can be performed if I is not available)
Limited Clinical Chemistry	ALT, AST, Bilirubin total, BUN, hs-CRP [#] , hs-CTnI (hf-CTnT) [#] , LDH, NT-proBNP [#]

Test Category	Test Name
Lipid Panel	HDL Cholesterol, LDL Cholesterol, Total Cholesterol, Triglycerides
CCI	
Urine Chemistry	Urine albumin, urine creatinine, urine protein, urine albumin-creatinine ratio (UACR), urine albumin-protein ratio (UPCR)
*Urine microscopy/sediment (automatic or manual)	Bacteria, Casts (RTEC - Renal Epithelial Cell Casts, GC – Granular Casts, HC – Hyaline Casts, Erythrocyte Casts, - Leucocyte Casts)
Urine dipstick	Macroscopic Panel: Color, Bilirubin, Blood, Glucose, Ketones, Leukocytes (leucocyte esterase), Nitrite, pH, Protein, Specific Gravity, Urobilinogen
CCI	
Hepatitis testing	HBV or HBC serology tests
Liver Event Testing and Liver Follow-Up Testing	Albumin, ALP, ALT, AST, CK, GGT, GLDH, INR, PT, and Total Bilirubin (TBIL), Test for hemolysis (haptoglobin, reticulocytes, unconjugated [indirect] bilirubin. These tests are in addition to routine testing, to be performed only in follow-up to safety events when indicated in Section 10.5 Liver safety monitoring
Pregnancy Test	Serum pregnancy test Urine pregnancy test Confirmatory serum pregnancy required in case of positive urine pregnancy test

*To be performed if the test is available at the local lab.

** Type (fasting/non-fasting) to remain consistent throughout study

In case tests are not available at the local lab, discuss with Novartis regarding analysis of these safety BM parameters by Central Lab.

